#### Assessment of Intensity

The investigator will make an assessment of intensity for each AE and SAE reported during the study and assign it to 1 of the following categories:

- Mild: An event that is easily tolerated by the participant, causing minimal discomfort and not interfering with everyday activities.
- Moderate: An event that causes sufficient discomfort and interferes with normal everyday activities.
- Severe: An event that prevents normal everyday activities. An AE that is assessed as severe should not be confused with an SAE. Severe is a category utilised for rating the intensity of an event; and both AE and SAE can be assessed as severe.

An event is defined as 'serious' when it meets at least 1 of the predefined outcomes as described in the definition of an SAE, NOT when it is rated as severe.

#### **Assessment of Causality**

- The investigator is obligated to assess the relationship between study participation and each occurrence of each AE/SAE.
- A "reasonable possibility" of a relationship conveys that there are facts, evidence, and/or arguments to suggest a causal relationship, rather than a relationship cannot be ruled out.
- The investigator will use clinical judgment to determine the relationship.
- Alternative causes, such as underlying disease(s), concomitant therapy, and other risk factors, as well as the temporal relationship of the event to study participation will be considered and investigated.
- The investigator will also consult the Investigator's Brochure (IB) and/or Product Information, for marketed products, in his/her assessment.
- For each AE/SAE, the investigator must document in the medical notes that they

- have reviewed the AE/SAE and has provided an assessment of causality.
- There may be situations in which an AE/SAE has occurred, and the investigator has minimal information to include in the initial report to GSK. However, it is very important that the investigator always make an assessment of causality for every event before the initial transmission of the AE/SAE data to GSK.
- The investigator may change their opinion of causality in light of follow-up information and send an AE/SAE follow-up report with the updated causality assessment.
- The causality assessment is one of the criteria used when determining regulatory reporting requirements.

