#### 1.1. Benefit/Risk Assessment

#### 1.1.1. Risk Assessment

This study does not involve the administration of any study treatment intervention to participants nor invasive study procedures. No potential risks beyond the routine clinical practice are considered in relate to participating in this study.

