#### 2. OBJECTIVES/ENDPOINTS

The objective of this study is to collect and assess information on the long-term (2 to 4 years) safety and effectiveness of Nucala (mepolizumab 300 mg, subcutaneous administration) in patients with EGPA, who have already used Nucala for 96 weeks (approximately 2 years), in real-world settings in Japan.

Objectives	Endpoints
Primary	
To investigate the long-term safety of Nucala in adult patients with EGPA	• Frequency of Adverse events (AEs)/ serious adverse events (SAEs)
	• Frequency of AEs related to Nucala (adverse drug reactions, ADRs)
	• Frequency of AEs of special interests (AESI)
Secondary	
To investigate the long-term effectiveness of Nucala in adult patients with EGPA	• Proportion of participants with clinical symptoms as assessed by 9 organ-systems (i.e. systemic, skin, mucous membranes/eyes, ears/nose/throat, chest, cardiovascular, abdominal, renal, nervous system)
	• Proportion of participants with EGPA relapse a
	
 
Annualized rate (event/year) of hospitalization for EGPA-related events
 

	Annualized rate (event/year) of emergency

a. EGPA relapse is defined as any of the following with worsening EGPA. 1) Increased dose of OCS. 2) Initiation/increased dose of immuno-suppressive agents. 3) EGPA treatment with hospitalization (Section 4.6).

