#### 6.2.2. Method of Detecting AEs and SAEs

- The method of recording, evaluating, and assessing causality of AEs and SAEs and the procedures for completing and transmitting SAE reports are provided in Section 9.3 (Appendix 3).
- Care will be taken not to introduce bias when detecting an AE and/or an SAE. Openended and non-leading verbal questioning of the participant is the preferred method to inquire about the occurrence of AE.

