#### 9.3.4. Reporting of AE and SAE to GSK

#### AE and SAE Reporting to GSK via Electronic Data Collection Tool

- The primary mechanism for reporting AE/SAE to GSK will be the electronic data collection tool.
- If the electronic system is unavailable, then the site will use the paper SAE data collection tool (see next section) in order to report the event within 24 hours.
- The site will enter the SAE data into the electronic system as soon as it becomes available.
- The investigator or medically-qualified sub-investigator must show evidence within the eCRF (e.g., check review box, signature, etc.) of review and verification of the relationship of each SAE to study participation (causality) within 72 hours of SAE entry into the eCRF.
- After the study is completed at a given site, the electronic data collection tool will be taken off-line to prevent the entry of new data or changes to existing data.
- If a site receives a report of a new AE/SAE from a study participant or receives

213684

updated data on a previously reported AE/SAE after the electronic data collection tool has been taken off line, then the site can report this information on a paper SAE form (see next section).

• Contacts for AE/SAE reporting can be found in the SRM.

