4.2.2. Main analytical approach

The primary analyses will be based on the TP. Adverse events (AEs) will be coded using the Medical Dictionary for Regulatory Activities (MedDRA), with the maximum intensity of each AE determined by the investigator (as mild, moderate, severe or unknown).

All AEs, ADRs, SAEs, AEs leading to withdrawal from study, and AESIs will be summarized by the observation period and the total period (the observation period and the follow-up period), respectively. A separate summary of AEs by maximum intensity will be produced by the observation period and the total period, respectively.

The frequency and percentage of all AEs will be summarized and displayed in two ways: 1) in descending order by PT only and 2) in descending order by SOC and PT.

Separate summaries will be provided for ADRs. An ADR is defined as an AE for which the investigator classifies the possible relationship to study intervention as "Yes". A worst-case scenario approach will be taken to handle missing relatedness data, i.e. the summary table will include events with the relationship to study intervention as 'Yes' or missing. The summary table will be displayed by SOC and PT. The relationship of primary SOCs, Preferred Terms, and verbatim texts will be listed.

The number and percentage of participants who experienced the serious adverse event will be summarized.

The following will be considered adverse events of special interest (AESI) for the purpose of analyses: Hypersensitivity (including anaphylaxis), infections and malignant tumors, defined as safety specifications in the Japanese RMP.

AESI	Definition	Dictionary code
Hypersensitivity (including anaphylaxis)	Anaphylaxis reaction (SMQ/narrow)	20000021 (narrow)
	Excluding "10078117: Eosinophilic granulomatosis with polyangiitis" from PT contained in Hypersensitivity (SMQ/narrow)	20000214 (narrow)
Infections	Infections: Infections and infestations(MedDRA/J SOC)	MedDRA/J SOC: 10021881
Malignant tumors	Malignant tumors (SMQ/narrow)	20000227 (narrow) 20000228 (narrow)
	Lymphoma malignum (SMQ/narrow)	20000215 (narrow)

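### Protocol Appendix 3 asks for causality against study participation, but the primary ADR endpoint needs relationship to Nucala

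*Protocol*

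**What the plan says.** Protocol Section 6.2.2 sends the reader to Section 9.3 (Appendix 3) for "The method of recording, evaluating, and assessing causality of AEs and SAEs". Three instructions in that appendix set the object of the causal judgement:

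- Section 9.3.3, Assessment of Causality: "The investigator is obligated to assess the relationship between study participation and each occurrence of each AE/SAE".
- The same list, on alternative causes and timing: "as well as the temporal relationship of the event to study participation will be considered and investigated".
- Section 9.3.4, on the investigator's sign-off in the eCRF: "verification of the relationship of each SAE to study participation (causality").

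The endpoint these ratings feed is given in Protocol Section 2 and repeated in SAP Sections 1.1 and 4.2.1: "Frequency of AEs related to Nucala (adverse drug reactions, ADRs"). Protocol Section 1.1.1 states: "This study does not involve the administration of any study treatment intervention to participants nor invasive study procedures".

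SAP Section 4.2.2 uses a third term: "An ADR is defined as an AE for which the investigator classifies the possible relationship to study intervention as" *Yes*. It adds: "A worst-case scenario approach will be taken to handle missing relatedness data". An event with no rating is therefore counted as an ADR.

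**The concern.** In a trial that assigns the drug, participation and drug exposure come close to being the same thing. Here they are separate. Participants are already on marketed Nucala by their physician's decision, and the study only collects data from routine care. An infection or hypersensitivity reaction can be caused by Nucala and have nothing to do with enrolment. No passage says that *study participation* stands for Nucala.

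The rating decides which events count as ADRs, one of the three primary endpoint groups. If the eCRF question or a site follows the literal wording, drug reactions could be answered *No* and drop out of the ADR tables. Appendix 3 also notes that causality is one of the criteria for regulatory reporting.

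**Working it through.** No arithmetic on trial data applies, so the check is a count of terms and a side-by-side reading.

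**1. What Appendix 3 says.** *Study participation* occurs 3 times in the AE definition (Section 9.3.1), 2 times in Assessment of Causality (9.3.3) and once in the electronic reporting list (9.3.4): 3 + 2 + 1 = 6. The three in the AE definition only say what an AE is. The other 2 + 1 = 3 tell the investigator what to assess or verify. *Nucala* occurs 0 times in the appendix.

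**2. What the rest of the plan needs.** Leaving aside the endpoint statements themselves, these places require a judgement about the drug or product:

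| Place in the protocol | Causal object | Use |
|---|---|---|
| 6.2 | Nucala | responsibility for follow-up |
| 6.2.1 | Nucala | reporting within 5 work days; SAEs learned of after the study |
| 6.2.3 | Nucala | follow-up until resolution |
| 9.4 | Nucala | SAEs from post-study pregnancy, reported through Appendix 3 |
| 9.1, footnote 1 | drug | contact with the sponsor |
| 9.3.3, Follow-up of AEs and SAEs | drug | updated data within 5 work days |
| 6.3 | any GSK product | pharmacovigilance reporting |
| 9.6, roles and collection rows | any GSK product | collection and reporting |
| 9.6, timelines and final report rows | any GSK product | reporting and final summary |

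That is 4 naming Nucala, 2 naming the drug and 3 naming any GSK product: 4 + 2 + 3 = 9 places in eight sections, since Appendix 6 is counted twice. The total depends on how repeated statements are grouped; the contrast with the three instructions does not. Section 9.4 sends events judged related to Nucala to an appendix whose causality bullets ask about something else.

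**3. What the SAP analyses.** The SAP's term is *study intervention*. The study-design table in SAP 1.2 uses that label for the row describing Nucala, and Protocol Appendices 4 and 5 use it in the same sense. The only description of the analysed field therefore points to the drug.

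**4. What happens to a literal answer.** Under SAP 4.2.2 there are three cases:

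- rated *Yes*: counted as an ADR;
- rating missing: counted as an ADR;
- rated *No*: not counted.

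A drug reaction judged unrelated to participation falls in the third case, which the missing-data rule does not reach.

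**5. Which results are exposed.** Of the three primary endpoint groups (AEs/SAEs, ADRs, AESIs), only ADRs use the rating: 1 of 3. AESIs are selected by MedDRA terms, and all-AE and SAE counts take no account of relatedness.

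**The case against.** The strongest reply is that nobody would read the instruction literally. Appendix 3 sends the investigator to the Investigator's Brochure or Product Information, treats concomitant therapy as an alternative cause, and sets a deadline for drug-related AE data. Other sections oblige the same investigator to judge relatedness to Nucala anyway. Since participation carries no identified risk beyond routine practice, a literal reading would make nearly every answer *No*, which is implausible in use. The eCRF question is not in the documents, and the one description of the analysed field points to the drug.

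Most of this stands. It shows that the intent was relatedness to Nucala, and it means that no loss of ADRs can be inferred from the documents. It does not make the three bullets right. They are the operative text on causality, and one of them governs a sign-off inside the eCRF.

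A second objection is that the AE definition and the SAP's *study intervention* would remain after the change. The AE definition does not direct the causality rating, and the SAP term is used elsewhere for Nucala, so neither undermines the correction.

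**Conclusion.** The inconsistency is real and minor. Three causality instructions name *study participation* where the primary ADR endpoint and the safety-reporting rules need relationship to Nucala, the drug or a GSK product. Confidence in the wording conflict is high.

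The effect on the data cannot be determined, because the documents give neither the eCRF causality question nor an ADR rate. If the question names Nucala, the effect may be nil. ADRs would be under-counted only if the eCRF, or a site, follows the literal wording. The rule for reporting within 5 work days is already tied to Nucala.

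**What to change.** 1. **Check the eCRF causality question first.** SAP version 5.0 describes the interim database lock as already declared, so rewording the appendix alone would not change ratings already entered. If the question names Nucala, the entered ratings can stand. If it does not, query them; the SAP still places the final lock in the future.
2. **Then correct the wording.** Replace *study participation* with *Nucala* in the two causality bullets of Protocol 9.3.3 and in the SAE verification bullet of 9.3.4, and send sites a short clarification. Naming Nucala in the SAP 4.2.2 ADR definition at the same time would be a sensible tidy-up, but the correction does not depend on it.

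The cost is one look at the eCRF, a wording amendment submitted to the ethics committee (Protocol Section 6) and a brief notice to sites. Queries are an added cost only if the eCRF question does not name Nucala.

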#### Follow-up of AEs and SAEs

- The investigator is obligated to perform or arrange for the conduct of supplemental measurements and/or evaluations as medically indicated or as requested by GSK to elucidate the nature and/or causality of the AE/SAE as fully as possible. This may include additional laboratory tests or investigations, histopathological examinations, or consultation with other health care professionals.
- If a participant dies during participation in the study, the investigator will provide GSK with a copy of any post-mortem findings including histopathology.
- New or updated information will be recorded in the originally completed eCRF.
- The investigator will submit any updated SAE data to GSK within 24 hours of receipt of the information.
- The investigator will submit any updated drug related AE data to GSK within 5 work days of receipt of the information.

#### 9.3.4. Reporting of AE and SAE to GSK

#### AE and SAE Reporting to GSK via Electronic Data Collection Tool

- The primary mechanism for reporting AE/SAE to GSK will be the electronic data collection tool.
- If the electronic system is unavailable, then the site will use the paper SAE data collection tool (see next section) in order to report the event within 24 hours.
- The site will enter the SAE data into the electronic system as soon as it becomes available.
- The investigator or medically-qualified sub-investigator must show evidence within the eCRF (e.g., check review box, signature, etc.) of review and verification of the relationship of each SAE to study participation (causality) within 72 hours of SAE entry into the eCRF.
- After the study is completed at a given site, the electronic data collection tool will be taken off-line to prevent the entry of new data or changes to existing data.
- If a site receives a report of a new AE/SAE from a study participant or receives

213684

updated data on a previously reported AE/SAE after the electronic data collection tool has been taken off line, then the site can report this information on a paper SAE form (see next section).

• Contacts for AE/SAE reporting can be found in the SRM.

#### AE and SAE Reporting to GSK via Paper CRF

- Facsimile or email transmission of the AE/SAE paper CRF is the preferred method to transmit this information to the SAE coordinator.
- In rare circumstances and in the absence of facsimile equipment, notification by telephone is acceptable with a copy of the AE/SAE data collection tool sent by overnight mail or courier service.
- Initial notification via telephone does not replace the need for the investigator to complete and sign the AE/SAE CRF pages within the designated reporting time frames.
- Contacts for AE/SAE reporting can be found in the SRM.

# 9.4. APPENDIX 4: Collection of Pregnancy Information

#### Female Participants who become pregnant

- Investigator will collect pregnancy information on any female participant, who becomes pregnant while participating in this study.
- The initial information will be recorded on the appropriate form and submitted to GSK within 24 hours of learning of a participant's pregnancy.
- Participant will be followed to determine the outcome of the pregnancy. The investigator will collect follow up information on participant and neonate, which will be forwarded to GSK Generally, follow-up will not be required for longer than 6 to 8 weeks beyond the estimated delivery date.
- Any termination of pregnancy will be reported, regardless of fetal status (presence or absence of anomalies) or indication for procedure.
- While pregnancy itself is not considered to be an AE or SAE, any pregnancy complication or elective termination of a pregnancy for medical reasons will be reported as an AE or SAE.
- A spontaneous abortion (occurring at < 22 weeks gestational age) or still birth (occurring at > 22 weeks gestational age) is always considered to be an SAE and will be reported as such.
- Any SAE occurring as a result of a post-study pregnancy which is considered reasonably related to Nucala by the investigator, will be reported to GSK as described in Section 9.3 (Appendix 3). While the investigator is not obligated to actively seek this information in former study participants, he or she may learn of an SAE through spontaneous reporting.

Any female participant who becomes pregnant while participating may request continuation of study intervention.

# 9.5. APPENDIX 5: Medical Device Incidents: Definition and Procedures for Recording, Evaluating, Follow-up, and Reporting

#### **Definition and Documentation of Medical Device Incidents**

#### **Definitions of a Medical Device Incident**

#### **Medical Device Incident Definition**

• A medical device incident is any malfunction or deterioration in the characteristics and/or performance of a device as well as any inadequacy in the labeling or the instructions for use which, directly or indirectly, might lead to or might have led to the death of a participant/user/other person or to a serious deterioration in his/her state of health.

• Not all incidents lead to death or serious deterioration in health. The non-occurrence of such a result might have been due to other fortunate circumstances or to the intervention of health care personnel.

#### It is sufficient that:

- An **incident** associated with a device happened and
- The **incident** was such that, if it occurred again, might lead to death or a serious deterioration in health.

A serious deterioration in state of health can include any of the following:

- Life-threatening illness
- Permanent impairment of body function or permanent damage to body structure
- Condition necessitating medical or surgical intervention to prevent one of the above
- Fetal distress, fetal death, or any congenital abnormality or birth defects

#### **Examples of incidents**

- A participant, user, caregiver, or healthcare professional is injured as a result of a medical device failure or its misuse.
- A participant's study intervention is interrupted or compromised by a medical device failure.
- A misdiagnosis due to medical device failure leads to inappropriate treatment.
- A participant's health deteriorates due to medical device failure.

#### **Documenting Medical Device Incidents**

#### **Medical Device Incident Documenting**

- Any medical device incident occurring during the study will be documented in the
  participant's medical records, in accordance with the investigator's normal clinical
  practice, and on the appropriate form.
- For incidents fulfilling the definition of an AE or an SAE, the appropriate AE/SAE CRF page will be completed as described in Section 9.3 (Appendix 3).
- GSK will ask to investigator about medical device incidents to complete the form.
- It is very important that the investigator provides his/her assessment of causality (relationship to the medical device provided by GSK) at the time of the initial report and describes any corrective or remedial actions taken to prevent recurrence of the incident.

A remedial action is any action other than routine maintenance or servicing of a medical device where such action is necessary to prevent recurrence of an incident. This includes any amendment to the device design to prevent recurrence.

**CONFIDENTIAL** 

#### 9.6. **APPENDIX 6: STUDY-SPECIFIC PHARMACOVIGILANCE** PLAN (SPVP)

sPVP Element	Study-Specific Pharmacovigilance Plan (sPVP)				
	(tick applicable statements)				
Supplier/ Vendor PV training	
 
N/A – No supplier/vendor involved that could be in receipt of serious and/or non-serious AEs, pregnancy exposures, and/or incidents related to any GSK product
 
Supplier/vendor PV training will be conducted using the agreed method and current, approved content, prior to beginning the study. Training will be completed annually and documented.
 
				
Investigator and site staff PV training	
 
N/A – No Investigator and/or site staff involved that could be in receipt of serious and/or non-serious AEs, pregnancy exposures, and/or incidents related to any GSK product
 
Investigator and/or site staff PV training will be conducted using the agreed method and current, approved content, prior to beginning the study. Training will be completed annually and documented.
 
				
Safety-specific roles	☐ SAP is responsible for identifying, collecting, reporting and reconciling AEs, pregnancy exposures, and/or incidents related to any GSK product ☐ Investigator/monitoring staff is responsible for identifying, collecting, reporting and reconciling AEs, pregnancy exposures, and/or medical device incidents related to any GSK product				
AEs, pregnancy exposures, and incidents collection and reporting processes	
 
The following will be identified, collected, and reported to GSK Japan safety:         
 
serious and/or non-serious AEs, related to any GSK product
 
pregnancy exposures to any GSK product (note: in the case of a pregnancy registry, the registry will manage exposures)
 
incidents related to any GSK product
 
 
 
For studies that evaluate a GSK product, consult with SMG Pharma Safety SERM to determine if additional data is required and complete the information below:         
 
Study does not evaluate a GSK product - No additional study-specific safety data is to be collected
 
Study evaluates a GSK product - No additional study-specific safety data is to be collected
 
Study evaluates a GSK product - additional study-specific safety data is to be collected
 
 

				
AE, pregnancy exposure, and	GSK Global Adverse Event, Pregnancy Exposure, and Incident Reporting Form for Epidemiology and Health Outcome studies				

sPVP Element	Study-Specific Pharmacovigilance Plan (sPVP) (tick applicable statements)
incident collection forms	Alternative collection form(s) will be utilized Investigators will report using the following forms:  Adverse Event Report form (Japanese)
	Pregnancy Initial Notification Form (Japanese)
	Pregnancy Outcome Form (Japanese)
	Monitoring staff will report using the following forms: Safety Information Notification Form for CRAs (Japanese)
	Incident Information Notification Form (Japanese)
Frequency of data review	

N/A – No batch reviewing of the data.

☐ Batch review will be conducted

Reporting process and timelines for AEs, pregnancy exposures and medical device incidents	Severe adverse events, pregnancy exposures, and/or incidents related to any GSK product will be reported to SMG Pharma Safety within 24 hours of awareness of the event. Adverse events will be reported to SMG Pharma Safety within 5 work days of awareness of the event.
Interim study reports	
 
N/A – No interim study reports are planned.
 
☐ Interim study reports will be shared with the SERM product specialist / physician for review of the interim report safety data
 

Reconciliation process	A log of all AEs, pregnancy exposures, and incidents identified during the research will be provided to GSK central safety (for multiple country studies) or local safety (for single country studies) on a Reconciliation Form. Central or local safety will confirm all reports listed on the log are included on the GSK Safety Database.
Study-specific PVP monitoring process	
 
         ⊠ SAP will review the sPVP elements and discuss during regular study team and/or supplier meetings to ensure the plan is working effectively.     
 
         Other, please describe.     
 

Provision of final study report	A summary of AEs, pregnancy exposures, and/or incidents related to any GSK product will be included in the final study report. The final draft study report will be provided to the SERM product specialist / physician for review and approval where a specific asset is involved.

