# 6.2.1. Time Period and Frequency for Collecting AE and SAE Information

All AEs should be monitored throughout the study. All AEs and SAEs must be recorded in the eCRF.

All AEs and SAEs will be collected from the signing of the informed consent form until the final study visit.

All SAEs will be recorded and reported to the sponsor or designee within 24 hours of recognition, as indicated in Section 9.3 (Appendix 3). The investigator will submit any updated SAE data to the sponsor within 24 hours of it being available. AEs related to Nucala will be recorded and reported to the sponsor or designee within 5 work days of recognition.

Investigators are not obligated to actively seek AE/SAEs after the conclusion of the study participation. However, if the investigator learns of any SAE, including a death, at any time after a participant has been discharged from the study, and they consider the event to be reasonably related to Nucala, the investigator must promptly notify the sponsor. As for death information, investigators are asked to report it to the sponsor throughout the study period regardless of whether the death is related to Nucala or not.

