# 6.3. Adverse Event (AE), Pregnancy Exposure, and Incident Reporting Related to Any GSK Product

All serious and non-serious AEs, pregnancy exposures, or incidents related to any GSK product will be collected and reported as described in the study-specific pharmacovigilance plan (sPVP). The sPVP is provided in Section 9.6 (Appendix 6). This plan will include the following elements to ensure a comprehensive approach to safety event collection and reporting:

- Supplier pharmacovigilance training
- Investigator and site staff pharmacovigilance training
- Safety-specific roles
- AEs, pregnancy exposures, and incidents collection and reporting processes
- AE, pregnancy exposure, and incident collection forms
- Frequency of data review
- Reporting process and timelines
- Interim reports
- Reconciliation process
- Study-specific PVP monitoring process
- Provision of final study report

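### Appendix 6 ties the 24-hour reporting clock to severe events, while Section 6.2.1 and Appendix 3 tie it to serious events, so the timelines contradict each other

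*Protocol*

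**What the plan says.** Protocol Section 6.2.1 sets two clocks for the investigator. For serious events: "All SAEs will be recorded and reported to the sponsor or designee within 24 hours of recognition". For related events: "AEs related to Nucala will be recorded and reported to the sponsor or designee within 5 work days of recognition". Appendix 3 repeats the 24 hours for updated SAE data. It also keeps 24 hours when the electronic system is down and the paper SAE tool has to be used.

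Appendix 3, under the assessment of intensity, defines severe as the top of a three-level intensity scale and adds: "An AE that is assessed as severe should not be confused with an SAE". Seriousness is decided by outcome: "An event is defined as 'serious' when it meets at least 1 of the predefined outcomes".

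Appendix 6, in the row on reporting process and timelines, says: "Severe adverse events, pregnancy exposures, and/or incidents related to any GSK product will be reported to SMG Pharma Safety" within 24 hours of awareness. The next sentence begins "Adverse events will be reported to SMG Pharma Safety within" and gives 5 work days. Serious events are not mentioned in that row.

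Section 6.3 states that serious and non-serious adverse events related to any GSK product are collected and reported according to the plan in Appendix 6. It names the reporting process and timelines as one of that plan's elements.

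**The concern.** The row that Section 6.3 sends staff to uses an intensity term where the rest of the protocol uses an outcome term. The protocol defines the two as different things, so they cannot be read as synonyms.

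A serious event that is not severe is a realistic case. Appendix 3 counts inpatient hospitalisation as serious whatever the intensity, asks for doubtful hospitalisations to be treated as serious, and gives malignant cancers as an example of a serious event. Infections and malignant tumours are events of special interest within the primary endpoint.

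What is at stake is the timeliness of expedited safety reports in a study whose primary objective is safety. A site or vendor trained on Appendix 6 could report a moderate-intensity SAE on the slower clock and pass a check against Appendix 6 while breaching Section 6.2.1. It could also expedite severe events that the main text does not ask to be expedited.

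**Working it through.** There is no sample size, rate or error probability to reproduce. The check sets the clocks side by side for each combination of seriousness and intensity.

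**Inputs**
- Section 6.2.1: all SAEs, 24 hours; AEs related to Nucala, 5 work days.
- Appendix 3: updated SAE data, 24 hours; updated drug-related AE data, 5 work days; paper back-up for SAEs, 24 hours.
- Appendix 6, timeline row: severe adverse events, pregnancy exposures and incidents, 24 hours; adverse events, 5 work days.
- Appendix 3, intensity: every AE and SAE is rated mild, moderate or severe, independently of seriousness.

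**Scope.** Appendix 6 collects events related to a GSK product. Pregnancy exposures and incidents have 24 hours there in any case, so they are set aside. The comparison below is for a Nucala-related event outside those two classes.

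| Event | Section 6.2.1 | Appendix 6, as worded | Result |
|---|---|---|---|
| Serious, severe | 24 hours | 24 hours | agree |
| Serious, mild or moderate | 24 hours | 5 work days | conflict |
| Non-serious, severe | 5 work days | 24 hours | conflict, reversed |
| Non-serious, mild or moderate | 5 work days | 5 work days | agree |

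A Nucala-related SAE meets both sentences of Section 6.2.1. The table uses the 24-hour one because it covers all SAEs.

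For an event related to a GSK product other than Nucala, the second row is unchanged. The two non-serious rows then have no clock in Section 6.2.1, because its 5-work-day sentence names only Nucala.

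**Size of the gap.** Five work days that span one weekend are 5 + 2 = 7 calendar days, against 1 day. This assumes no public holiday.

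**Precedence.** Section 6.2.1 refers to Appendix 3 for SAE reporting. Section 6.3 refers to Appendix 6 for product-related events, serious ones included. A product-related SAE falls under both, and nothing says which prevails.

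**Intent.** Elsewhere Appendix 6 does use the outcome term. Its training rows speak of staff who could be "in receipt of serious and/or non-serious AEs, pregnancy exposures, and/or incidents related to any GSK product". The word in the timeline row is therefore probably a slip for *serious*, but it sits in the one row that sets the clock.

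**The case against.** The strongest reply is that the 24-hour duty for SAEs is unconditional in Section 6.2.1 and repeated in Appendix 3, and that nothing in Appendix 6 releases a site from it. An investigator who follows the whole protocol reports every SAE within 24 hours. This stands. A reader might infer that the plan permits a 5-work-day delay, or that Section 6.3 lets Appendix 6 override Section 6.2.1. The documents say neither.

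The scope is also limited. A reader might infer that every serious, non-severe event is affected. Events judged unrelated to any GSK product fall outside the Appendix 6 collection and keep 24 hours under Section 6.2.1 alone. Pregnancy exposures and incidents keep 24 hours in both places.

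The named recipients differ: the sponsor or its designee in Section 6.2.1, and a safety department in Appendix 6. Appendix 6 also lists separate forms for investigators and monitoring staff. The row could describe a later hand-off. The documents do not say that it does, and Section 6.3 presents the plan as governing collection and reporting in general. The possibility lowers confidence about the practical effect, but the wording still conflicts.

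Finally, a reader might infer that SAE data could be incomplete. That is not supported. All AEs and SAEs go into the eCRF, and Appendix 6 requires a log of events to be reconciled with the safety database. The effect is on timing only.

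**Conclusion.** The Appendix 6 timeline row is wrong as written and should be corrected. It contradicts Section 6.2.1 and Appendix 3 in two of the four combinations: serious events of mild or moderate intensity, and, for Nucala-related events, severe events that are not serious. The clocks differ by 24 hours against 5 work days, in opposite directions.

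This rests on reading *severe* as Appendix 3 defines it, and it applies only to product-related events that are not pregnancy exposures or incidents. The duty to report all SAEs within 24 hours is made ambiguous, not removed. How many events would be affected cannot be derived, because the documents give no expected split of SAEs by intensity or relatedness. The endpoint analyses are not affected.

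**What to change.** Reconcile the Appendix 6 timeline row with Section 6.2.1 and the Appendix 3 definitions:

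1. In the 24-hour sentence, replace *Severe adverse events* with *Serious adverse events*.
2. In the 5-work-day sentence, replace *Adverse events* with *Non-serious adverse events related to any GSK product*. Limiting it to Nucala would leave non-serious events related to other GSK products without a timeline, in a plan whose stated scope is any GSK product.
3. Reflect the corrected row in the pharmacovigilance training for sites and vendors.

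The cost is two short wording changes in one appendix row and a note in the training material. Data collection, the eCRF and the SAP are unchanged.
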